## **4.2.2 Subsequent Infusions**

Eligibility for the subsequent infusions of investigational product will be determined by the investigator based on clinical assessment (eg, assessments of hemodynamic status, directed physical examination if clinically indicated, and AE assessment) and review of local and / or central laboratory values according to the following criteria (Sections 4.2.2.1 and 4.2.2.2). In addition, the investigator should review the results of any available local and central laboratory ALT, total bilirubin and serum creatinine results from specimens drawn before or after the previous infusion before administering a subsequent infusion of the investigational product.

Note: During the course of study conduct, the IDMC will determine whether the requirement for local and / or central laboratory assessments of hepatic and / or renal function before subsequent infusions may be discontinued (ie, blood sampling and review of results can stop). In that case, all subsequent infusions are to be based on clinical assessment (ie, starting with infusion 2 [Visit 3]).

Each infusion of investigational product should be completed as close to the visit windows outlined in the [Schedule of Assessments](#) as possible. An infusion may be skipped (ie, 'missed') or delayed at the discretion of the investigator to evaluate and treat an AE before the next infusion. The time window between each infusion may be extended as long as the last infusion of investigational product is given within 30 days of infusion 1 and the minimum window between infusions is at least 5 days.

### **4.2.2.1 Key Hepatic Laboratory Requirements before Subsequent Infusions**

For assessment of hepatic function before infusion 2, 3, or 4, the following criteria must be met by investigator review of central laboratory values obtained from the previous visits:

- ALT value must be  $\leq 3 \times$  ULN and total bilirubin value must be  $\leq 2 \times$  ULN for dosing eligibility.
- If the ALT value is  $> 3 \times$  ULN and total bilirubin value is  $> 2 \times$  ULN, or if the ALT value is  $> 5 \times$  ULN then infusion must be delayed.
  - A repeat assessment by local laboratory should be performed once at least 24 hours later to assess hepatic stability and dosing eligibility. Additionally, a blood sample must be sent to the central laboratory for study analysis purposes.

- If the ALT value is  $> 3 \times \text{ULN}$  and  $\leq 5 \times \text{ULN}$ , or the total bilirubin value is  $> 2 \times \text{ULN}$ , the investigator should perform a clinical assessment using all available data (including assessment of symptoms consistent with liver dysfunction, including right upper quadrant abdominal pain, anorexia, etc.), which may include a repeat laboratory assessment.
  - If the elevation in ALT or total bilirubin is not related to the investigational product and an alternate nonserious etiology is known, the infusion may be administered at the discretion of the investigator.
  - If the repeat ALT value is  $> 3 \times \text{ULN}$  and total bilirubin value is  $> 2 \times \text{ULN}$ , or if the repeat ALT value is  $> 5 \times \text{ULN}$ , then subject should be discontinued from further dosing.

If clinically significant abnormal laboratory test results are identified after investigational product infusion, the test(s) should be repeated until laboratory values return to normal and / or baseline for hepatic function, as per Section 8.1.3.1.1.2, and are reported as AEs as per [Section 9](#).

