### **8.1.3.2.2      Central Laboratory Testing**

Blood for the clinical laboratory tests presented in [Table 3](#) is to be obtained from the subject as outlined in the [Schedule of Assessments](#). Before infusion 2, 3, and 4, the ALT, total bilirubin and serum creatinine criteria must be met by review of central laboratory (obtained from the previous visits) by the investigator as indicated in [Sections 4.2.2.1](#) and [4.2.2.2](#). Any additional testing is considered part of standard of care and / or unscheduled visit at the discretion of the investigator to assess subject safety.

Clinical laboratory test results (serum biochemistry and hematology) from the central and / or local laboratory that are outside the normal reference range and are deemed clinically significant by the investigator are to be recorded as AEs ([Section 9.6](#)) or SAEs ([Section 9.6.3](#)). Refer to [Table 3](#) for specific serum biochemistry and hematology parameters for testing. If clinically significant abnormal laboratory test results are identified after

investigational product infusion, the test(s) will be repeated until the values return to normal and / or baseline. Safety parameters should be repeated if the specimen is hemolyzed.

Investigators must review all laboratory results to assess for clinical significance and to determine if values meet criteria for AEs ([Section 9.1.1](#)).

Refer to the Laboratory Manual for details about the collection, storage, handling, and transportation of biological specimens.

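### Protocol 4.2.2.1: the delay bullet and the discretionary-dosing bullet both apply to every combined ALT and bilirubin elevation, and the discretionary bullet also departs from the mandatory eligibility limits

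*Protocol*

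**What the plan says.** Protocol Section 4.2.2.1 governs re-dosing on hepatic grounds. Its lead-in says that "the following criteria must be met by investigator review of central laboratory values obtained from the previous visits". Three bullets follow:

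- **Eligibility bullet.** ALT at most 3×ULN and total bilirubin at most 2×ULN are required "for dosing eligibility".
- **Delay bullet.** If ALT is above 3×ULN and bilirubin is above 2×ULN, or if ALT is above 5×ULN, "then infusion must be delayed". Beneath it: "A repeat assessment by local laboratory should be performed once at least 24 hours later to assess hepatic stability and dosing eligibility".
- **Assessment bullet.** If ALT is above 3 and up to 5×ULN, or bilirubin is above 2×ULN, "the investigator should perform a clinical assessment using all available data", with a repeat test optional. Two sub-bullets are printed beneath it. Under the first, where the rise is judged unrelated to product and another, nonserious cause is known, "the infusion may be administered at the discretion of the investigator". Under the second, dosing stops if the repeat shows the combined elevation again or ALT above 5×ULN.

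Protocol Section 8.1.3.2.2 says that before infusions 2, 3 and 4 "the ALT, total bilirubin and serum creatinine criteria must be met by review of central laboratory" values, and refers back to Sections 4.2.2.1 and 4.2.2.2.

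**The concern.** Three bullets that look like a graded scheme should divide subjects into separate groups. These do not. The assessment bullet is triggered by bilirubin above 2×ULN with no condition on ALT, and nothing confines it to isolated elevations or to subjects not already caught by the delay bullet. A subject with both values raised therefore meets a mandatory delay and a conditional permission to dose. The assessment bullet also opens dosing to subjects whom the eligibility bullet rules out.

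What is at stake is a clear dosing instruction. The combination in the overlap is one that Protocol Section 9.6.2.2 requires to be reported as a serious adverse event within 24 hours. Section 3.1 plans for about 1000 sites, so an instruction that can be read two ways may be applied unevenly, and it would be unclear how to classify such an infusion as a protocol deviation.

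**Working it through.** The documents give no figure to reproduce. The check is logical: write each trigger as a condition, then list the combinations. ALT and bilirubin (TB) are in multiples of ULN, and the thresholds are those of Section 4.2.2.1.

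- E (eligible): ALT ≤ 3 and TB ≤ 2
- D (delay): (ALT > 3 and TB > 2) or ALT > 5
- A (assessment, with discretionary dosing available): (3 < ALT ≤ 5) or TB > 2

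| ALT | TB | E met | D applies | A applies | D and A together | A applies though E fails |
|---|---|---|---|---|---|---|
| ≤ 3 | ≤ 2 | yes | no | no | no | no |
| ≤ 3 | > 2 | no | no | yes | no | **yes** |
| > 3 to 5 | ≤ 2 | no | no | yes | no | **yes** |
| > 3 to 5 | > 2 | no | yes | yes | **yes** | **yes** |
| > 5 | ≤ 2 | no | yes | no | no | no |
| > 5 | > 2 | no | yes | yes | **yes** | **yes** |

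**Delay against assessment.** If ALT > 3 and TB > 2, D holds through its first limb and A holds through its bilirubin limb. In the other direction, if TB ≤ 2, D needs ALT > 5 while A needs ALT ≤ 5, which is impossible; if ALT ≤ 3, D fails. So D and A coincide exactly when ALT > 3 and TB > 2. That is 2 of 6 combinations, and they include every combined elevation. ALT of 4 with TB of 3, and ALT of 6 with TB of 3, are examples.

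**Assessment against eligibility.** A requires ALT > 3 or TB > 2, and either one fails E. The discretionary permission therefore reaches only subjects outside the stated limits: 4 of 6 combinations, two of them isolated elevations.

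**Delay against eligibility.** D requires ALT > 3, which already fails E. Delaying a subject who is not eligible agrees with the limits: 0 of 6 combinations conflict.

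**Repeat test.** The delay bullet calls for a repeat, but the stated outcome of a repeat is printed under the assessment bullet. If that bullet excludes delayed subjects, their repeat has no stated outcome. If it includes them, its discretionary permission includes them too. The nesting may be an artefact of reading the PDF. The overlap above does not depend on it, because it follows from the thresholds alone.

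**Comparison.** The creatinine rules in Section 4.2.2.2 use bands of < 0.3, 0.3 to 0.5 and > 0.5 mg/dL, which do not overlap.

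**The case against.** The best case for the text is that the assessment bullet was meant as a residual tier. Its ALT cap of 5×ULN makes most sense if higher values have already been dealt with, and its sub-bullet speaks of a rise in one analyte or the other. The eligibility bullet can be read as a general rule with a stated exception: Section 4.2.2.2 uses a similar form, a mandatory lead-in followed by a tier that calls for judgement. Section 4.2.3 also sends sites to study reference manuals on delayed infusions, which may already settle the matter and cannot be seen here. This shows that the intent is probably recoverable. It does not supply the missing words: neither document says that the third bullet excludes subjects caught by the second, or which of the two governs.

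A reader might infer four stronger things that the documents do not support:

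- **That the delay bullet also contradicts the eligibility limits.** It applies only to subjects who already fail them.
- **That one site could dose and another hold the same subject, both fully compliant.** A site that holds breaches neither bullet. A site that doses without delay breaches the mandatory one, whatever the permissive one says.
- **That the discretionary branch allows dosing in potential Hy's law cases.** Section 9.1.2.2 requires confirmation on repeat, no cholestasis and no other explanation. A subject correctly placed in the discretionary branch has a known alternative cause and so falls outside that definition. The 24-hour rule in Section 9.6.2.2 concerns reporting and neither allows nor forbids an infusion.
- **That Section 8.1.3.2.2 is a separate contradiction.** It refers back to Section 4.2.2.1, so it repeats the mandatory wording and brings in the same three bullets.

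**Conclusion.** The point holds as a defect of wording in a dosing rule. The delay and assessment bullets both apply to every subject with ALT above 3×ULN and bilirubin above 2×ULN, with no stated precedence. Separately, the discretionary permission, but not the delay, is inconsistent with the eligibility limits, including for isolated elevations.

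The counts of 2 and 4 out of 6 are combinations of thresholds, not shares of subjects. The documents give no frequency for the combined elevation. SAP Section 4.6.1.2 cites 2.7% on placebo in AEGIS-I for ALT above 3×ULN at any time up to Day 29. If that rate carried over, it would be a ceiling for the combined group, which must also have bilirubin above 2×ULN, and have it before infusion 2, 3 or 4. How far below the ceiling the group lies is not stated, but few subjects are likely to be affected. The rule would also lapse if the data monitoring committee recommended ending laboratory review before later infusions, as Section 4.2.2 allows.

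No endpoint, alpha, power or estimand is touched. The conclusion rests on the printed thresholds and on the absence of a precedence statement in these two documents. It takes no view on which instruction is clinically right.

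**What to change.** The sponsor should reconcile the three bullets of Protocol Section 4.2.2.1 so that each combination of ALT and bilirubin falls under exactly one instruction, and state whether the discretionary permission is an exception to the eligibility limits. The text should also make clear which subjects the repeat-test outcome applies to. The cross-reference in Section 8.1.3.2.2 should then be aligned with the revised wording. Which instruction applies to which combination is a clinical decision for the sponsor.

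The cost is a protocol wording change and a clarification to sites, with the study reference manuals checked for consistency. No analysis, sample size or boundary in the SAP changes. If dosing is already complete, the same clarification is still worth recording for the classification of protocol deviations under SAP Section 9.2.

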#### **4.2.2.2 Key Renal Laboratory Requirements before Subsequent Infusions**

Before infusion 2, for subjects who received infusion 1 of investigational product  $> 12$  hours and  $< 48$  hours after IV contrast administration, a local laboratory serum creatinine value should be obtained before the infusion for comparison with the local laboratory baseline value and reviewed by the investigator. A blood sample for local laboratory testing to assess dosing eligibility for infusion 2 should not occur earlier than 72 hours following infusion 1.

- If the serum creatinine value is increased  $< 0.3 \text{ mg/dL}$  ( $27 \mu\text{mol/L}$ ) from the baseline serum creatinine value, then the subject is eligible for dosing.
- If the serum creatinine value is increased between  $0.3$  and  $0.5 \text{ mg/dL}$  ( $27 \mu\text{mol/L}$  and  $44 \mu\text{mol/L}$ ) from the baseline serum creatinine value and it may be attributable to changes in concomitant medications with potential renal effect or other clinical factors (eg, IV fluid discontinued), or falls within range of variability previously observed for the subject as per investigator's discretion and there is no suspicion of AKI, then the subject is eligible for dosing. A repeat creatinine assessment should be performed prior to the next infusion / visit. If variation cannot be attributable to clinical factors as listed above, the infusion should be delayed and repeat assessment of serum creatinine is performed.
- If the serum creatinine value is increased  $> 0.5 \text{ mg/dL}$  ( $44 \mu\text{mol/L}$ ) from the baseline serum creatinine value, then dosing of infusion 2 must be delayed.

**Apolipoprotein A-I**

---

- A repeat assessment by local laboratory should be performed once at least 24 hours later to assess renal stability for study and dosing eligibility. Additionally, a blood sample must be sent to the central laboratory for study analysis purposes.
- If the repeat serum creatinine value is increased  $> 0.5$  mg/dL (44  $\mu$ mol/L) from the baseline serum creatinine value (ie, the elevation is confirmed), then the infusion and subsequent infusions must be discontinued.

If clinically significant abnormal laboratory test results are identified after investigational product infusion, the test(s) should be repeated until laboratory values return to normal and / or baseline for renal function, and are reported as AEs per [Section 9](#).

Before infusion 2, for subjects who received infusion 1 of investigational product  $\geq 48$  hours after FMC or IV contrast administration, eligibility for dosing will be determined by the investigator based on clinical assessment (eg, assessments of hemodynamic status, directed physical exam if clinically indicated, and AE assessment) with support of local and central laboratory serum creatinine values at baseline.

Before infusions 3 and 4, all subjects must meet the following criteria based on a review of central laboratory values from the previous visits (infusions 2 and 3, respectively) compared with the central laboratory baseline value:

- If the serum creatinine value is increased  $< 0.3$  mg/dL (27  $\mu$ mol/L) from the baseline serum creatinine value, then the subject is eligible for dosing.
- If the serum creatinine value is increased between 0.3 and 0.5 mg/dL (27  $\mu$ mol/L and 44  $\mu$ mol/L) from the baseline serum creatinine value and it may be attributable to changes in concomitant medications with potential renal effect or other clinical factors (eg, IV fluid discontinued), or falls within range of variability previously observed for the subject as per investigator's discretion and there is no suspicion of AKI, then the subject is eligible for dosing. A repeat creatinine assessment should be performed prior to the next infusion / visit. If variation cannot be attributable to clinical factors as listed above, the infusion should be delayed and repeat assessment of serum creatinine should be performed.
- If the serum creatinine value is increased  $> 0.5$  mg/dL (44  $\mu$ mol/L) from the baseline serum creatinine value, then dosing of the infusion must be delayed.
  - A repeat assessment by local laboratory must be performed once at least 24 hours later to assess renal stability for study and dosing eligibility. Additionally, a blood sample must be sent to the central laboratory for study analysis purposes.

- If the repeat serum creatinine value is increased  $> 0.5$  mg/dL (44  $\mu$ mol/L) from the baseline serum creatinine value, then the infusion and all subsequent infusions should be discontinued.

If clinically significant abnormal laboratory test results are identified after investigational product infusion, the test(s) should be repeated until laboratory values return to normal and / or baseline for renal function, and are reported as AEs as per [Section 9](#).

#### **4.2.3 Infusion Delay**

Each infusion of investigational product should be completed as close to the visit windows outlined in the [Schedule of Assessments](#) as possible. An infusion may be skipped (ie, ‘missed’) or delayed at the discretion of the investigator to evaluate and treat an AE before the next infusion. The time window between each infusion may be extended as long as the last infusion of investigational product is given within 30 days of infusion 1 and the minimum window between infusions is at least 5 days.

Refer to the study reference manuals for detailed instructions for how to address study procedures performed in the Active Treatment Period and for detailed instructions for skipped (ie, ‘missed’) or delayed infusion.

### **4.3 Discontinuation of Treatment and / or Subject Withdrawal from the Study**

Subjects may withdraw from treatment at any time but will continue in follow-up: every subject, including those who prematurely stop taking investigational product, will be followed for vital status and MACE endpoint assessments and complete study procedures as specified in the protocol unless they explicitly withdraw consent from follow-up ([Section 4.3.3](#)). The requirements for handling early discontinuations from investigational product are described below. Details of the requirements for subject follow-up are provided in [Section 4.3.4](#). All efforts should be made to confirm vital status for all subjects up to the end of his / her follow-up.

#### **4.3.1 Early Discontinuation of Investigational Product**

Subjects may request at any time that further investigational product administration be discontinued, or it may be discontinued at any time at the discretion of the investigator or CSLB for safety, behavioral, or administrative reasons (eg, due to an AE, protocol deviation, or study termination). In accordance with International Council for Harmonisation (ICH)

principles of Good Clinical Practice (GCP), the investigator always has the option to advise a subject to stop further administration of investigational product if the subject's safety or well-being is compromised by the continued administration of investigational product.

Concern for the interests of the subject must always prevail over the interests of the study.

If a subject permanently discontinues treatment with investigational product (regardless of the reason) before the end of the planned Active Treatment Period, the subject will undergo an investigational product Early Termination Visit (Visit 6) and continue safety and MACE endpoint follow-up according to the [Schedule of Assessments](#) and [Section 4.3.4](#). If the discontinuation occurs at a scheduled visit, the assessments and procedures for the investigational product Early Termination Visit (Visit 6, [Schedule of Assessments](#)) should be completed instead of that visit.

If a subject discontinues investigational product (regardless of the reason) between scheduled visits, the subject should be brought into the clinic as soon as possible to complete the investigational product Early Termination Visit / Visit 6 assessments. All subjects should continue follow-up visits for MACE endpoint assessment ([Section 4.3.4](#)).

In all cases, reasons for discontinuation of investigational product and the date of last dose will be recorded.

#### **4.3.2                    Possible Reasons for Discontinuation of Investigational Product**

Possible reasons for subject discontinuation from investigational product include, but are not limited to, the following:

- Adverse event resulting in discontinuation.
- Subject becomes pregnant during the study.
- Need for chronic use of a prohibited concomitant medication, ie, chemotherapy or other investigational product ([Section 7.3](#)).
- Decision by subject or proxy.
- Sponsor terminated study.
- Investigative site closed and subject was unable to transfer to another investigative site.

### **4.3.3                   Subject Withdrawal from the Study**

Subjects who no longer wish to attend study visits in person will be asked to be contacted for follow-up by telephone or other methods identified below to assess MACE endpoints and vital status. Similarly, subjects who withdraw consent will be asked if they can be contacted at the end of the study to determine vital status, at a minimum. This change to follow-up from in-clinic visits to by telephone or other methods does not constitute subject withdrawal from the study.

Subject withdrawal from the study is defined as the subject's withdrawal of consent from further participation in the study, including any contact by the study site personnel to determine the MACE endpoints and vital status of the subject. Subjects may withdraw from the study at any time at their own request, or they may be withdrawn at any time at the discretion of the investigator or CSLB for safety, behavioral, or administrative reasons (eg, due to an AE, protocol violation, subject noncompliance, and study termination). In accordance with ICH principles of GCP, the investigator always has the option to advise a subject to withdraw from the study if the subject's safety or well-being is compromised by his or her further participation in the study. Concern for the interests of the subject must always prevail over the interests of the study. If a subject is withdrawn from the study by the investigator or further participation is declined by the subject, they will continue to have access to medical care and will be treated as per routine medical practice.

When a subject is contemplating withdrawal from the study, the investigator (in addition to the coordinator) should discuss with the subject the importance of further follow-up and how further follow-up information can be obtained through telephone contact, registered mail contact, contact through referring physician(s), family or friends, or utilization of publically available information. This latter source is the only available option for subjects who withdraw consent. All efforts should be made to confirm vital status at minimum.

Information regarding study outcomes or vital status will be collected if it is available in the public domain, and if it is permitted by local and national law, according to the specific provision included in the signed informed consent. Alternative permitted options to obtain study outcomes and vital status (eg, healthcare providers and / or relatives) will be summarized on a checklist to be provided to all sites participating in the study separate from the protocol; these permitted options are also subject to local and national law. For any subject who withdraws consent for contact by the study site personnel, the reason for withdrawal of consent will be recorded in the eCRF; the investigator will document / sign the

checklist, and describe the discussion with the subject regarding each of the contact methods that were offered. The discussion must be documented.

Withdrawal from the study as a result of an AE and any therapeutic measures that are taken shall be at the discretion of the investigator. If a subject withdraws from the study for any reason, any ongoing AEs will be followed until resolution, until deemed stable by the investigator, or until the subject is deemed by the investigator to be lost to follow-up.

If the subject withdraws from the study, CSLB will retain and continue to use any data collected before such withdrawal of consent, in accordance with prevailing regulatory guidance.

